1.2 Number of Display Digits

Item	Definition
Percentage (%)	Rate of patients with ADRs: Indicated by rounding off to the second decimal place. Other than above: Indicated by rounding off to the first decimal place.
Summary statistics	Mean value: Indicated by rounding off to the first digit below the raw numerical data. Standard deviation: Indicated by rounding off to the second digit below the raw numerical data. First quartile, median, third quartile: Indicated by rounding off to the first digit below the raw numerical data. Minimum value, maximum value: Indicated at the same digits of the raw numerical data.
Confidence interval	Indicated by rounding off to the second digit below the raw numerical data.

1.3 Confidence Coefficient

Two-sided 95%

1.4 Handling of Evaluation Timepoint Data

The evaluation timepoints are the start of treatment with the Drug (baseline), Month 3, Month 6, Month 9, Month 12, and final evaluation timepoint.

If multiple data exist within each evaluation timepoint, calculate absolute values of difference in measurement intervals from the basic day count and adopt the minimum absolute value as date for that evaluation timepoint. If all the absolute values are the same, adopt one for the latest date of testing/measurement. Test/Measurement values should not be adopted that have been obtained after completion of treatment with the Drug. The final evaluation timepoint test/measurement should be one taken on the latest date within 405 days elapsed since the start date (including values tested/measured during washout period). Note that the number days elapsed since the start date should be counted with the start date as day 0 and the previous day as day -1.

Evaluation Timepoint	Tolerance (Number of Days Since Baseline)	Basic Day Count
Baseline	-90 to 0	0
Month 3	1 to 135	90
Month 6	136 to 225	180
Month 9	226 to 315	270
Month 12	316 to 405	360
Final evaluation timepoint	1 to 405	–

2.0 Results of Special Drug Use Surveillance (Survey 1)

<Lotriga Granular Capsules Special Drug Use Surveillance [long-term use survey]>

2.1 Patient Breakdown (Patient Disposition)

Statistical Analysis Set	Enrolled patients in this special drug use surveillance
Details of Statistical Analysis	
Number of enrolled patients, number of patient enrollment sites, number of patients with eCRFs collected, number of patients with eCRFs uncollected, number of locked patients, number of unlocked patients, number of safety-evaluable patients, number of safety-unevaluable patients, number of efficacy-evaluable patients, number of efficacy-unevaluable patients
 
Do not double-count the same medical institution with different participating clinical departments when counting the number of patient enrollment sites.
 
Count the number of patients per reason below for not collecting and total the numbers when the number of patients with eCRFs uncollected.
 
<Reasons for not collecting>
 
 • Survey under way • eCRFs uncollectable • Investigator transferred • Investigator’s health reasons • Patients enrolled 15 days after Drug prescription [before eCRF collection] • Others 
Count the number of patients per reason below for exclusion and total the numbers when counting the numbers of safety- and efficacy-unevaluable patients. If the same patient falls under multiple reasons for exclusion, they should be counted separately.
 
<Reasons for exclusion from safety evaluation>
 
 • Drug administered before contract period • Patient enrolled 15 days after Drug prescription • No data available after Drug administration • Drug not administered 
<Reasons for exclusion from efficacy evaluation>
 
 • Other than target disease • Exclusion criteria violation 
No output needs to be generated for items for which the number of patients is zero.
 
For periodic safety reports, the numbers of efficacy-evaluable and unevaluable patients should not be counted.

Figure/Table No.	Figure 2.1, Table 2.1

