1.0 Definitions of Terms

1.1 Definitions

Item	Definition
Survey unit period (periodic safety report)	Periodic Safety Report 1: July 22, 2012 to January 21, 2013 Periodic Safety Report 2: January 22, 2013 to July 21, 2013 Periodic Safety Report 3: July 22, 2013 to January 21, 2014 Periodic Safety Report 4: January 22, 2014 to July 21, 2014 Periodic Safety Report 5: July 22, 2014 to July 21, 2015 Periodic Safety Report 6: July 22, 2015 to July 21, 2016 Periodic Safety Report 7: July 22, 2016 to July 21, 2017 Periodic Safety Report 8: July 22, 2017 to July 21, 2018
Drug	Lotriga Granular Capsules
SOC	System organ class of MedDRA.
HLGT	High level group term of MedDRA.
PT	Preferred term of MedDRA.
LLT	Lowest level term of MedDRA.
Enrolled patient	A patient approved for enrollment in the Study.
Patient with eCRF collected	An enrolled patient whose eCRF was submitted via CCI .
Patient with eCRF uncollected	An enrolled patient other than a patient with eCRF collected.
Locked patient	A patient who has completed the approval process in the PMS system.
Unlocked patient	A patient with eCRF collected other than a locked patient.
Safety-evaluable patient	A locked patient included in safety evaluation.
Safety-unevaluable patient	A locked patient excluded from safety evaluation.
Efficacy-evaluable patient	A safety-evaluable patient included in efficacy evaluation.
Efficacy-unevaluable patient	A safety-evaluable patient excluded from efficacy evaluation.
ADR	An abbreviated form of the term ‘adverse drug reaction or infection.’ Refers to an adverse event other than those judged by the investigator as ‘not related’ in causality to the Drug. In this plan, ‘adverse drug reactions or infections’ is used in headings, and ‘ADRs’ is used in the text and tables.
Serious adverse event (SAE)	[Prior-approval data] An adverse event (AE) judged as ‘serious’ by the trial investigator. [Surveillance data] An adverse event (AE) judged as ‘serious’ by the investigator. Note that events listed in the separate MedDRA code list of the Takeda Medically Significant AE List should be treated as serious even if judged as

Item	Definition
	'not serious' by the investigator.
Bleeding-related event	An event falling under Standardized MedDRA Query (SMQ) code 20000038 (hemorrhagic SMQ [narrow scope]).

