2.4.39 Summary of Onset Status of Serious Adverse Events in Safety-Unevaluable patients

Statistical Analysis Set	Safety-unevaluable patients in this special drug use surveillance	
Details of Statistical Analysis	Compile the following items.	
	Item Name	Details of Statistical Analysis
	Number of study sites	Number of medical institutions that have collected eCRFs
	Number of surveyed patients	Number of safety-unevaluable patients.
	Number of patients	Number of patients with SAEs
	Number of SAEs	Number of SAEs Every PT occurring should be counted as one event.
	Rate of patients	Calculated by the following equation: $[\text{Number of Patients with SAEs}] / [\text{Number of Safety-unevaluable Patients}] \times 100$.
	SAE type	
The calculation method in performing each analysis should be as follows:
 
[Number of patients with SAEs]
 
 • Number of patients in which SAEs occurred. 
[Number of SAEs]
 
 • Number of SAEs that occurred. If the same SAE occurs more than once in the same patient, a total of frequencies of the SAE should be counted. 
[SAE type]
 
 • SAEs should be replaced by MedDRA terms. Categorize by SOC and compile SAEs by PT in each category. If SOC is 'Investigations,' classify by HLGT (sort by HLGT code in ascending order but without outputting) and compile SAEs by PT. 
 • At SOC level, the numbers and rates of patients with SAEs should be presented by SOC internationally agreed order. If the same SOC occurs more than once in the same patient, SAEs should be counted as one patient in the SOC. 
At PT level, the numbers of patients with SAEs should be presented by PT code in ascending order. If the same PT occurs more than once in the same patient, SAEs should be counted as one patient in the PT.

		The number of SAEs of which causal relationship to the Drug has been denied should be entered in the [] brackets. In that case, if the same PT events which are both "related" and "not related" in causality to the Drug occur in the same patient, the SAEs should be counted as one patient in the "related" category.
Figure/Table No.	Table 2.4.39	

2.4.40 Summary of Onset Status of Serious Adverse Drug Reactions or Infections in Safety-Unevaluable patients

Statistical Analysis Set	Safety-unevaluable patients in this special drug use surveillance	

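### SAP 2.1 totals exclusion reasons rather than patients, so the unevaluable count is too high whenever an excluded patient has more than one reason (minor)

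*SAP*

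**What the plan says.** SAP 2.1 asks for several disposition items, among them "number of safety-evaluable patients, number of safety-unevaluable patients, number of efficacy-evaluable patients, number of efficacy-unevaluable patients". For the unevaluable groups it then gives a counting instruction: "Count the number of patients per reason below for exclusion and total the numbers when counting the numbers of safety- and efficacy-unevaluable patients". The next sentence deals with overlap: "If the same patient falls under multiple reasons for exclusion, they should be counted separately". Four reasons are listed for exclusion from safety evaluation and two for exclusion from efficacy evaluation.

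SAP 1.1 defines the groups by patient. Safety-evaluable: "A locked patient included in safety evaluation". Safety-unevaluable: "A locked patient excluded from safety evaluation". Efficacy-unevaluable: "A safety-evaluable patient excluded from efficacy evaluation".

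The safety-unevaluable count reappears later. In 2.4.39 the surveyed patients are given as "Number of safety-unevaluable patients", and the rates in 2.4.39 and 2.4.40 divide by the same term.

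**The concern.** The two sentences in SAP 2.1 do not fit together if the result is meant to be a number of patients. Adding reason rows gives the number of patients only when the rows are mutually exclusive, and the second sentence makes them non-exclusive.

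Overlap is realistic. The SAP expects it, since it writes a rule for it. Two of the safety reasons can easily coincide: dosing that began before the site's contract, and enrolment 15 or more days after prescription. Protocol 7.3 allows enrolment only for prescriptions since the contract start, entered within 14 days. If a site enters patients only once its contract has begun, a patient prescribed the Drug 15 or more days before that date meets both reasons.

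At stake is the patient-flow figure and table, which would not add up. Protocol 10.1 asks for the number of patients excluded and for the reasons, and these are two different counts.

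**Working it through.** The plan states no disposition figure, so there is nothing to reproduce. The check is a counting identity, followed by an illustration on assumed values.

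**Notation.** U is the number of distinct safety-unevaluable patients, r_i the number of reasons for patient i, S the sum of the reason counts, E the number of safety-evaluable patients and L the number of locked patients.

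**Step 1, what SAP 2.1 yields.** S = Σ r_i = U + Σ(r_i − 1). Hence S = U only if every excluded patient has exactly one reason.

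**Step 2, what SAP 1.1 requires.** The two safety groups partition the locked patients, so E + U = L. Substituting the 2.1 total gives E + S = L + Σ(r_i − 1). The surplus is the number of extra reasons.

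**Step 3, efficacy.** The same identity holds one level down. The efficacy groups partition the safety-evaluable patients, so their counts must sum to E, not to L.

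**Step 4, illustration.** Assumptions: L = 3,000 (the target in Protocol 3.1, used only for scale), U = 100, so E = 2,900. Some patients have exactly two reasons. The last column assumes 5 patients with a serious adverse event and assumes that S is used as the denominator; the correct rate is 5/100 = 5.00%.

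| Share with two reasons | S | E + S | Surplus over L | 5/S |
|---|---|---|---|---|
| 0% | 100 | 3,000 | 0 | 5.00% |
| 5% | 105 | 3,005 | 5 | 4.76% |
| 10% | 110 | 3,010 | 10 | 4.55% |
| 20% | 120 | 3,020 | 20 | 4.17% |
| 30% | 130 | 3,030 | 30 | 3.85% |

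At 20% overlap, U = 30 gives S = 36 and U = 150 gives S = 180. The relative overstatement is 20% at each U, because it depends only on the overlap.

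**Step 5, after the fix.** Counting each patient once gives 2,900 + 100 = 3,000 whatever the overlap.

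**The case against.** The strongest reply is that a coherent reading exists. SAP 2.1 lists the numbers of unevaluable patients as items in their own right, and SAP 1.1 defines those terms by patient. The instruction to total may mean no more than to tabulate by reason beneath a headline of distinct patients. Listing a patient under each applicable reason is ordinary practice. This stands as a reason to call the point a conflict between an instruction and a definition, and not a demonstrated wrong total. It does not remove the conflict. The SAP states single-count rules where it wants them: for sites it says "Do not double-count the same medical institution with different participating clinical departments when counting the number of patient enrollment sites", and in the event tables a patient with a repeated term counts once. The disposition total has no such rule. The earliest SAP version in the file has the totalling instruction without the sentence on multiple reasons; later versions added that sentence and left the instruction alone.

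A reader might also infer that the rates in 2.4.39 and 2.4.40 are biased downward. The documents do not support that. Both tables use the term defined in SAP 1.1 and do not refer to the sum in 2.1. Tables 2.4.2 and 2.4.4 specify no rate for unevaluable patients.

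Nor should the overlap be taken as general. The reason concerning absence of data after administration presupposes that the Drug was given, so as worded it does not overlap with the reason that the Drug was never given. Late enrolment found before the eCRF is collected is also listed as a reason for non-collection. Those patients are never locked, which narrows the overlap that remains.

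**Conclusion.** The wording should be corrected, and the point is minor. Followed literally, SAP 2.1 produces a count of reasons that exceeds the count of patients whenever reasons overlap, against the definitions in SAP 1.1. For an assumed 100 unevaluable patients with 0% to 30% having two reasons, the reported total is 100 to 130, and the safety counts exceed locked patients by 0 to 30. Both the 100 and the overlap share are assumptions.

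It would go too far to say that the count is overstated as a matter of fact: that needs at least one patient with several reasons, and no counts are given. Rates in 2.4.39 and 2.4.40 would be affected only if the 2.1 total were carried forward as denominator. Rates in safety-evaluable patients are not affected, because that group is defined directly and the SAP does not derive it by subtraction.

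**What to change.** Replace the two sentences in SAP 2.1 with wording such as: The numbers of safety- and efficacy-unevaluable patients count each patient once. Reasons are tabulated separately; a patient with several reasons appears under each, so the reason rows may sum to more than the patient total.

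Add two checks to the disposition program:

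- safety-evaluable + safety-unevaluable = locked;
- efficacy-evaluable + efficacy-unevaluable = safety-evaluable.

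State in 2.4.39 and 2.4.40 that the denominator is the number of distinct safety-unevaluable patients.

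The cost is a short SAP edit and two lines of program checking. No new data are needed.

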2.2 Patient Demographics

Statistical Analysis Set	Safety-evaluable patients in this special drug use surveillance																							
Details of Statistical Analysis	
Categorize the patient population by the following categories for each item and compile the number of patients and incidence.
 
  
 Item Name	Category	
   
 Sex	Male, Female	
 
 Age	Summary statistics	
 
 Minimum age to 64 years, 65 to 74 years, 75 years to maximum age, Unknown	
 
 Treatment category	Outpatient, inpatient	
 
 BMI	Summary statistics	
 
 Less than 18.5 kg/m², 18.5 to less than 25 kg/m², 25 to less than 30 kg/m², 30 kg/m² or over, unknown	
 
 Complications	No, Yes	
 
 Complication breakdown	Hypertension, Diabetic, Liver disorder, Kidney disorder, Cardiac disorders [myocardial infarction, angina pectoris, atrial fibrillation, others], Cerebrovascular diseases [hemorrhagic cerebrovascular disease, ischemic cerebrovascular disease, others], Bleeding-related event, Others	
 
 Drinking history (Does the patient drink alcoholic beverages nearly every day?)	Yes, No, Unknown	
 
 Fasting triglyceride at baseline (mg/dL)	Less than 150 mg/dL, 150 to less than 400 mg/dL, 400 to less than 500 mg/dL, 500mg/dL or over, Not measured	
 
 Less than 150 mg/dL, 150 to less than 400mg/dL, 400 to less than 500 mg/dL, 500 to less than 750 mg/dL, 750 mg/dL or over, Not measured	
 
 Random triglyceride at baseline (mg/dL)	Less than 150 mg/dL, 150 to less than 400 mg/dL, 400 to less than 500 mg/dL, 500mg/dL or over, Not measured	
  
	Item Name	Category	Sex	Male, Female	Age	Summary statistics	Minimum age to 64 years, 65 to 74 years, 75 years to maximum age, Unknown	Treatment category	Outpatient, inpatient	BMI	Summary statistics	Less than 18.5 kg/m ² , 18.5 to less than 25 kg/m ² , 25 to less than 30 kg/m ² , 30 kg/m ² or over, unknown	Complications	No, Yes	Complication breakdown	Hypertension, Diabetic, Liver disorder, Kidney disorder, Cardiac disorders [myocardial infarction, angina pectoris, atrial fibrillation, others], Cerebrovascular diseases [hemorrhagic cerebrovascular disease, ischemic cerebrovascular disease, others], Bleeding-related event, Others	Drinking history (Does the patient drink alcoholic beverages nearly every day?)	Yes, No, Unknown	Fasting triglyceride at baseline (mg/dL)	Less than 150 mg/dL, 150 to less than 400 mg/dL, 400 to less than 500 mg/dL, 500mg/dL or over, Not measured	Less than 150 mg/dL, 150 to less than 400mg/dL, 400 to less than 500 mg/dL, 500 to less than 750 mg/dL, 750 mg/dL or over, Not measured	Random triglyceride at baseline (mg/dL)	Less than 150 mg/dL, 150 to less than 400 mg/dL, 400 to less than 500 mg/dL, 500mg/dL or over, Not measured
Item Name	Category																							
Sex	Male, Female																							
Age	Summary statistics																							
	Minimum age to 64 years, 65 to 74 years, 75 years to maximum age, Unknown																							
Treatment category	Outpatient, inpatient																							
BMI	Summary statistics																							
	Less than 18.5 kg/m ² , 18.5 to less than 25 kg/m ² , 25 to less than 30 kg/m ² , 30 kg/m ² or over, unknown																							
Complications	No, Yes																							
Complication breakdown	Hypertension, Diabetic, Liver disorder, Kidney disorder, Cardiac disorders [myocardial infarction, angina pectoris, atrial fibrillation, others], Cerebrovascular diseases [hemorrhagic cerebrovascular disease, ischemic cerebrovascular disease, others], Bleeding-related event, Others																							
Drinking history (Does the patient drink alcoholic beverages nearly every day?)	Yes, No, Unknown																							
Fasting triglyceride at baseline (mg/dL)	Less than 150 mg/dL, 150 to less than 400 mg/dL, 400 to less than 500 mg/dL, 500mg/dL or over, Not measured																							
	Less than 150 mg/dL, 150 to less than 400mg/dL, 400 to less than 500 mg/dL, 500 to less than 750 mg/dL, 750 mg/dL or over, Not measured																							
Random triglyceride at baseline (mg/dL)	Less than 150 mg/dL, 150 to less than 400 mg/dL, 400 to less than 500 mg/dL, 500mg/dL or over, Not measured																							

		Less than 150 mg/dL, 150 to less than 400mg/dL, 400 to less than 500 mg/dL, 500 to less than 750 mg/dL, 750 mg/dL or over, Not measured
	Smoking history	Never, Current, Former, Unknown
	Hypersensitivity disposition	No, Yes, Unknown
	Disease duration	Summary statistics
		Less than 1 year, 1 to less than 3 years, 3 to less than 5 years, 5 years or over, Unknown
	Presence or absence of surgery within one month before baseline	No, Yes
	Pregnancy status during treatment (only for female)	No, Yes
Figure/Table No.	Table 2.2	

2.3 Treatment Details

Statistical Analysis Set	Safety-evaluable patients in this special drug use surveillance																								
Details of Statistical Analysis	
Categorize the patient population by the following categories for each item and compile the number of patients and incidence.
 
  
 Item Name	Category	
   
 Initial dose	2 g, 4 g, Other	
 
 Change in daily dose	No, Yes	
 
 Breakdown of change in daily dose	2 g → 4 g, 4 g → 2 g, Other	
 
 Mean daily dose	Less than 2 g, 2 to less than 4 g, 4 to less than 6 g, 6 g or over	
 
 Treatment duration	1 to 30 days, 31 to 90 days, 91 to 180 days, 181 to 360 days, 361 days or over	
 
 Presence or absence of concomitant antihyperlipidemic drug use (during observation period)	No, Yes	
 
 Breakdown of concomitant antihyperlipidemic drugs (during observation period)	Statins drugs, fibrate drugs, intestinal transporter inhibitors, anion-exchange resin, nicotinic acid derivatives, probucol, ethyl icosapentate (EPA), others	
 
 Presence or absence of concomitant anticoagulant/antiplatelet drug use (during observation period)	No, Yes	
 
 Breakdown of concomitant anticoagulant/antiplatelet drugs (during observation period)	Anticoagulant drugs, antiplatelet drugs	
 
 Completion of treatment with the Drug	No, Yes	
 
 Reason for treatment	Treatment goal achieved, AE developing, Patient no	
  
	Item Name	Category	Initial dose	2 g, 4 g, Other	Change in daily dose	No, Yes	Breakdown of change in daily dose	2 g → 4 g, 4 g → 2 g, Other	Mean daily dose	Less than 2 g, 2 to less than 4 g, 4 to less than 6 g, 6 g or over	Treatment duration	1 to 30 days, 31 to 90 days, 91 to 180 days, 181 to 360 days, 361 days or over	Presence or absence of concomitant antihyperlipidemic drug use (during observation period)	No, Yes	Breakdown of concomitant antihyperlipidemic drugs (during observation period)	Statins drugs, fibrate drugs, intestinal transporter inhibitors, anion-exchange resin, nicotinic acid derivatives, probucol, ethyl icosapentate (EPA), others	Presence or absence of concomitant anticoagulant/antiplatelet drug use (during observation period)	No, Yes	Breakdown of concomitant anticoagulant/antiplatelet drugs (during observation period)	Anticoagulant drugs, antiplatelet drugs	Completion of treatment with the Drug	No, Yes	Reason for treatment	Treatment goal achieved, AE developing, Patient no
Item Name	Category																								
Initial dose	2 g, 4 g, Other																								
Change in daily dose	No, Yes																								
Breakdown of change in daily dose	2 g → 4 g, 4 g → 2 g, Other																								
Mean daily dose	Less than 2 g, 2 to less than 4 g, 4 to less than 6 g, 6 g or over																								
Treatment duration	1 to 30 days, 31 to 90 days, 91 to 180 days, 181 to 360 days, 361 days or over																								
Presence or absence of concomitant antihyperlipidemic drug use (during observation period)	No, Yes																								
Breakdown of concomitant antihyperlipidemic drugs (during observation period)	Statins drugs, fibrate drugs, intestinal transporter inhibitors, anion-exchange resin, nicotinic acid derivatives, probucol, ethyl icosapentate (EPA), others																								
Presence or absence of concomitant anticoagulant/antiplatelet drug use (during observation period)	No, Yes																								
Breakdown of concomitant anticoagulant/antiplatelet drugs (during observation period)	Anticoagulant drugs, antiplatelet drugs																								
Completion of treatment with the Drug	No, Yes																								
Reason for treatment	Treatment goal achieved, AE developing, Patient no																								

	completion	longer visiting hospital due to hospital transfer or otherwise, Insufficient effect, Other
Figure/Table No.	Table 2.3	

